## 5.1 Subject Inclusion Criteria

All must be answered YES for the subject to be eligible for study participation:

- 1. Subject reads and signs the Informed Consent Form (ICF) and agree to have bronchoscopy with bronchoalveolar lavage under sedation or light anesthesia and comply with study procedures.
- 2. Healthy male or non-pregnant, non-lactating female subjects 18 to 45 years of age (both inclusive) at the time of dosing.
  - a. Note 1: Determined by medical history (MH), medication use, physical examination (PE), and vital signs, clinical laboratory tests and 12-lead ECG within reference ranges at Screening and Day-2. (See Sections 8.1 and 8.2, Appendix B, Table 2, Table 3 and Table 4 and the study-specific MOP.)

Exceptions to BP, HR and laboratory test values being with normal ranges are:

- Abnormal HR and BP on first measurement may be repeated twice more with the subject resting between measurements for at least 5 min according to Section 8.1.6.
- Subjects with baseline  $HR \ge 45$  to 50 bpm may be accepted if otherwise healthy adults with known history of asymptomatic bradycardia.
- Subjects with baseline SBP up to 140 mmHg and DBP up to 90 mmHg may be accepted if otherwise healthy.
- A laboratory value that is Grade 1 will be allowed if not considered to be clinically significant by the investigator, with the exception of ALT, AST, AP, BUN, urine protein, serum creatinine or estimated glomerular filtration rate (eGFR) <70 mL/min /1.73 m^2 by the Chronic Kidney Disease Epidemiology collaboration (CKD-EPI) equation.
- 3. Female subjects of childbearing potential should use highly effective methods of contraception from the time of screening to 30 days after dosing.
  - Note 1: A female is considered of childbearing potential unless post-menopausal (defined as history of ≥1 year of spontaneous amenorrhea and a FSH level >40 IU/L), or permanently surgically sterilized.

- Note 2: Highly effective contraceptive methods include: (a) surgical sterilization methods, such as tubal ligation, bilateral oophorectomy, salpingectomy, hysterectomy, or successful tubal obliteration (e.g., Essure®) with documented radiological confirmation test at least 90 days after the procedure, or (b) long-acting reversible contraception, such as progestin-releasing subdermal implants, copper intrauterine devices (IUDs), levonorgestrel-releasing IUDs.

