#### 9.2.3 Procedures to be Followed in the Event of Abnormal Laboratory Test Values or Abnormal Clinical Findings

A licensed study clinician (listed on FDA Form 1572) will determine seriousness, severity, and causality of abnormal laboratory values; provide a medical evaluation of TEAEs; and classify TEAEs based upon medical judgment.

Abnormal laboratory values or clinical findings for all enrolled subjects after dosing will be assessed using the toxicity scales in Appendix B. Out of range values and findings noted at screening or baseline, but allowable for enrollment and dosing if within Grade 1, will only be considered TEAEs if their severity increases to Grade 2 or higher. For abnormalities noted from the time of study drug dosing, any Grade 1 or higher laboratory abnormality listed on the toxicity Table 3 in Appendix B will be entered in the database as a TEAE. Safety laboratory results that are reported as TEAEs will be evaluated by the CTU clinician as clinically significant (CS) or not clinically significant (NCS). Abnormal laboratory values, performed as part of HEM, COAG, CHEM, or UA but not listed in this toxicity table will be evaluated by the study clinicians, recorded in the source document and, if clinically significant, considered TEAEs and graded according to the criteria in Section 9.2.1.

Protocol-specific laboratory normal range values are included in the study-specific MOP and toxicity grades for evaluation of TEAEs are included in Appendix B, Table 3.

Gross blood in urine that is confirmed due to menses is not a TEAE (but is for all other reasons).

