#### Secondary:

- Type and incidence of treatment-emergent adverse events (TEAEs) and serious AEs (SAEs) to Day 30 (± 4 days) after dosing.
- Frequency of clinically significant TEAEs in physical examination (PE) findings and of changes from baseline in vital signs and clinical laboratory parameters until Day 14 (± 3 days) after dosing.
- Frequency of changes in electrocardiogram (ECG) intervals (QTcF, PR, QRS, heart rate [HR]), and of morphological changes from baseline until 24 ± 1 h after dosing.

• Type and incidence of TEAEs related to auditory (cochlear) function tests (pure-tone audiometry and distortion product otoacoustic emissions [DPOAEs]) to Day 30 (± 4 days) after dosing.

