#### 4.5.1. Safety Variables

Incidence, relatedness, and severity of TEAEs and SAEs will be recorded from the time of dosing through the Final Visit on Day 30 ( $\pm$  4 days), or early termination. All AEs will be graded for severity and the relationship to the study product, as described in protocol v3.0 Section 9.2. Clinical AEs will be graded using the toxicity grading scales in Table 3.

Abnormal clinical laboratory, VS, and ECG results will be assessed using the toxicity grading scales in Table 4, Table 5, and Table 6, respectively. Audiology results will be graded according to the toxicity grading scales in Table 3.

In addition to AEs, the following safety endpoints will be assessed at baseline and each post-dose timepoint collected. For continuous parameters, change from baseline will also be summarized for all post-dose timepoints. For definitions of baseline for safety endpoints, refer to Section 3.3.3.

- Clinical safety laboratory evaluations (CHEM, HEM, COAG, UA)
  - Clinical laboratory tests will be performed at Screening, Check-In (Day -2), pre-dose on Day 1, Day 2 (24 h post-dose), Day 3 (48 h post-dose), and Day 14.
  - The following parameters will be measured:

- CHEM: sodium, potassium, glucose (fasting), BUN, creatinine, eGFR, calcium, chloride, magnesium, total carbon dioxide, albumin, total protein, AP, ALT, AST, total bilirubin, direct bilirubin, thyroid stimulating hormone (TSH), free thyroxine (T4), and free triiodothyronine (T3)
- HEM: hemoglobin, hematocrit, platelets, WBC count, and differential WBC count (neutrophils, lymphocytes, eosinophils, basophils, and monocytes)
- COAG: activated partial thromboplastin time (aPTT), prothrombin time (Protime), and international normalized ratio (INR)
- UA: urine dipstick, including protein, glucose, occult blood, and urine microscopy, including WBC count, RBC count, and bacteria, if urine dipstick is abnormal
- Additionally, tests for exploratory biomarkers for renal injury, serum cystatin C, urinary KIM-1, and KIM-1 normalized per mg urinary creatinine, will be performed at Check-In (Day -2), predose on Day 1, Day 3 (48 hours post-dose), Day 14, and Day 30.
- VS
  - VS will be measured at Screening, Check-In (Day -2), Day -1, Day 1 (pre-dose and 0.5 h, 1 h, 4 h, and 16 h post-dose), Day 2 (24 h and 36 h post-dose), Day 3 (48 h and 60 h post-dose), and Day 14.
  - The following parameters will be measured: systolic BP, diastolic BP, HR, respiratory rate, and oral temperature.

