### 14.3.4 Abnormal Laboratory Value Listings (by Participant)

### Table 23: Listing of Abnormal Laboratory Results – Chemistry

[Implementation Note: This listing is included in the table shells document, as it is included in the body of the CSR. This listing includes all abnormal Chemistry results (laboratory results outside of the normal range defined in the protocol). Normal chemistry results for other parameters that occurred on the same visit as the abnormal result will not be listed. Results that are outside the normal range but not mild, moderate, or severe will have "(ONR)" included after the result. Similarly, results that meet grading criteria of mild, moderate, or severe but which are not treatment emergent (not worse than baseline) will be shown as ONR. Listing should be sorted by Cohort, Participant ID, Timepoint, and Parameter.]

Cohort	Participant ID	Sex	Age (years)	Planned Study Day	Actual Study Day	Laboratory Parameter (Units)	Result (Severity)	Clinical Significance	Relationship to Treatment	If Not Related, Alternate Etiology	Action Taken with Study Treatment	Participant Discontinued Due to Result?

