# Table 50:Kidney Function Biomarker Summary Statistics Measurement and Change from
Baseline by Parameter and Timepoint – Safety Subset Population

### 14.3.6 Displays of Vital Signs

### Table 51: Vital Sign Toxicity Grade by Parameter, Timepoint, and Severity – Safety Population

[Implementation Note: If there is not at least one mild, moderate, or severe result with a parameter, then only the "Baseline" and "Maximum Severity Post Baseline" rows will be shown for that parameter. Toxicities representing an increase in the laboratory result will be summarized separately from decreases.]

			Mi Gra	ild / ide 1	Mod Gra	erate/ ide 2	Sev Gra	ere/ de 3
Parameter	Time Point	Ν	n	%	n	%	n	%
Any Parameter	Baseline	x	х	XX	х	XX	x	XX
	Maximum Severity Post Baseline	x	х	XX	х	XX	x	XX
	Day 1, 0.5 h Post-Dose	x	х	XX	х	XX	x	XX
	Day 1, 1 h Post-Dose	x	х	XX	х	XX	x	XX
	Day 1, 4 h Post-Dose	x	х	XX	х	XX	x	XX
	Day 1, 16 h Post-Dose	x	х	xx	х	XX	x	XX
	Day 2, 24 h Post-Dose	x	х	XX	х	XX	х	XX
	Day 2, 36 h Post-Dose	x	х	XX	х	XX	х	XX
	Day 3, 48 h Post-Dose	x	х	XX	х	XX	х	XX
	Day 3, 60 h Post-Dose	x	х	xx	х	XX	x	XX
	Day 14	x	х	XX	х	XX	х	XX
Systolic Blood Pressure, Decrease	Baseline	x	х	XX	х	XX	х	XX
	Maximum Severity Post Baseline	x	х	xx	х	XX	x	XX
		x	х	XX	х	XX	х	XX
		x	х	XX	х	XX	x	XX

Notes: N = Number of participants in the Safety Population with the vital sign assessed at the respective timepoint. Baseline = The most recent measurement prior to start of infusion. The "Maximum Severity Post Baseline" rows indicate the maximum severity experienced by each participant at any time point post baseline, including unscheduled assessments.

Table with similar format:

Table 52:Vital Sign Toxicity Grade by Parameter, Timepoint, and Severity – Safety Subset
Population

				Measu	rement			Change fr	om Baseline	
Parameter	Timepoint	Ν	Mean	SD	Median	Min, Max	Mean	SD	Median	Min, Max
Systolic Blood Pressure (mmHg)	Baseline	х	XX.X	XX.X	XX.X	xx, xx	-	-	-	-
	Day 1, 0.5 h Post-Dose	х	XX.X	XX.X	XX.X	xx, xx	XX.X	XX.X	XX.X	xx, xx
	Day 1, 1 h Post-Dose	х	XX.X	XX.X	XX.X	xx, xx	XX.X	XX.X	XX.X	xx, xx
	Day 1, 4 h Post-Dose	х	XX.X	XX.X	XX.X	xx, xx	XX.X	XX.X	XX.X	xx, xx
	Day 1, 16 h Post-Dose	х	XX.X	XX.X	XX.X	xx, xx	XX.X	XX.X	XX.X	xx, xx
	Day 2, 24 h Post-Dose	х	XX.X	XX.X	XX.X	xx, xx	XX.X	XX.X	XX.X	xx, xx
	Day 2, 36 h Post-Dose	x	XX.X	XX.X	XX.X	xx, xx	XX.X	XX.X	XX.X	xx, xx
	Day 3, 48 h Post-Dose	х	XX.X	XX.X	XX.X	xx, xx	XX.X	XX.X	XX.X	xx, xx

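### The 'Maximum Severity Post Baseline' row in the SAP toxicity-grade tables ignores each participant's own baseline grade and pools up to nine scheduled times against one, so carried-over grades are not separated from worsening

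*SAP*

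**What the plan says.** The note to SAP Table 51 says that the 'Maximum Severity Post Baseline' "rows indicate the maximum severity experienced by each participant at any time point post baseline, including unscheduled assessments". The notes to Tables 29 and 59 define the row in the same way. Tables 35-36, 41-42 and 47-48 inherit it by repeating Tables 29-30, and Tables 30, 52 and 60 share the format of their Safety Population counterparts. None of these notes requires the grade to be worse than the participant's own baseline. The Baseline row uses the most recent measurement before the infusion.

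For vital signs, SAP 4.5.1 schedules "Day 1 (pre-dose and 0.5 h, 1 h, 4 h, and 16 h post-dose", then "Day 2 (24 h and 36 h post-dose), Day 3 (48 h and 60 h post-dose), and Day 14". Laboratory tests are done at Screening and Check-In, then "pre-dose on Day 1, Day 2 (24 h post-dose), Day 3 (48 h post-dose), and Day 14". SAP 9.6, 9.7 and 9.8 keep unscheduled results out of the by-timepoint summaries but let them into the maximum.

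Protocol 5.1 allows some Grade 1 values at entry: "Subjects with baseline SBP up to 140 mmHg and DBP up to 90 mmHg may be accepted if otherwise healthy". It makes similar allowances for heart rate from 45 to 50 bpm and for many Grade 1 laboratory values. SAP Table 5 grades systolic pressure 131-150 mmHg, diastolic pressure 90-95 mmHg and heart rate 45-49 bpm as Grade 1.

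The chemistry listing, Table 23, handles the same situation differently: "results that meet grading criteria of mild, moderate, or severe but which are not treatment emergent (not worse than baseline) will be shown as ONR". Tables 24-26 repeat that rule for the other panels. For out-of-range findings allowed at entry, protocol 9.2.3 says they "will only be considered TEAEs if their severity increases to Grade 2 or higher".

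**The concern.** Two separate effects raise the Maximum Severity row above the Baseline row when the drug does nothing.

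The first is carry-over. A participant who enters at Grade 1 and stays there is tabulated as a post-baseline Grade 1. For a laboratory value, the same result would be shown as ONR in Tables 23-26 and as Mild in the matching grade table of the same study report.

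The second is the number of looks. The worst of nine sessions is compared with one session, and unscheduled readings enter only on the post-dose side. Protocol section 4 leaves unscheduled assessments after bronchoscopy to the pulmonologist's orders, so some of these readings will follow the procedure whatever the drug does.

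There is no control group against which to judge the rise. One secondary endpoint is the frequency "of changes from baseline in vital signs and clinical laboratory parameters". For vital signs and laboratory values, no planned table sets a participant's post-dose grade against that participant's own baseline grade. True worsening therefore cannot be read off the grade summaries.

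**Working it through.** The documents give no expected grade rates and no power calculation, so there is no planned figure to reproduce. The check has three steps.

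**1. Number of readings pooled, from SAP 4.5.1**

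- Vital signs: 0.5, 1, 4, 16, 24, 36, 48 and 60 h and Day 14, so k = 9.
- ECG: 1, 4, 16, 24, 36, 48 and 60 h and Day 14, so k = 8.
- Laboratory: 24 h, 48 h and Day 14, so k = 3.

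The Baseline row has one assessment in each case.

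**2. Size of the rise with no drug effect**

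Let p be the chance of Grade 1 or higher at one session. If readings within a person were independent, the maximum row would show 1 - (1 - p)^k. This is an upper bound, because readings within a person are correlated.

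- k = 9: p = 5% gives 1 - 0.95^9 = 37% (7.4 times baseline); 10% gives 61% (6.1 times); 20% gives 87% (4.3 times).
- k = 3: 5% gives 14.3% (2.9 times); 10% gives 27.1% (2.7 times); 20% gives 48.8% (2.4 times).

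A more realistic model assumes exchangeable normal readings with a threshold and a within-person correlation of 0.3 to 0.9. Both p and the correlation are assumptions. Each range below runs from correlation 0.3 to 0.9.

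| p | Vital signs (k = 9), maximum ÷ baseline | Laboratory (k = 3), maximum ÷ baseline |
|---|---|---|
| 5% | 5.8 to 2.3 | 2.6 to 1.6 |
| 10% | 4.7 to 2.0 | 2.4 to 1.5 |
| 20% | 3.5 to 1.75 | 2.2 to 1.4 |

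A systolic-pressure simulation applied the 140 mmHg entry limit, the SAP cut-points and the repeat-measurement rule of SAP 9.7. It assumed mean 115-125 mmHg, SD 10-12 and correlation 0.5-0.85. The ratio was 2.1 to 4.9. The repeat rule lowered both rows but barely changed their ratio.

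**3. Carry-over, and what a worse-than-baseline rule would do**

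Under the same assumptions, the chance that a participant at Grade 1 at baseline appears in the maximum row is:

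- 71-96% in the systolic model;
- 61-97% for a generic vital sign;
- 34-90% for a laboratory value.

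Take the systolic case with mean 120, SD 12, correlation 0.7 and the repeat rule on. The Baseline row shows 11.0%, or 2.2 of 20 participants. The maximum row shows 33.7%, or 6.7 of 20. Counting only grades worse than the participant's own baseline gives 24.8%, or 5.0 of 20, which is still about 2.2 times baseline. That rule removes carry-over but not the nine-look effect.

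Applied at a single timepoint with p = 10%, the same rule would show about 5% against a raw Baseline of 10% at correlation 0.7, and 3-8% over correlations 0.9 to 0.3. With no drug effect, that would look like improvement.

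**The case against.** The strongest reply is that this is one labelled and accurately footnoted row. The same tables carry a row for each scheduled time, and each of those is a fair one-look comparison with Baseline. Change from baseline is summarised in Tables 31-32, 37-38, 43-44 and 53-54 and, for ECG, in Tables 61-64. TEAEs are in Tables 15-20. The study is descriptive, with 20 participants and no hypothesis tests, and individual graded results are listed. All of this stands. A reader might infer that Baseline against Maximum Severity is the only frequency comparison available, and the documents do not support that.

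Other limits also stand:

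- A reader might infer a conflict with protocol 9.2.3. That section governs what is recorded as a TEAE, whereas these tables report grades. The inconsistency is with the display rule of Tables 23-26, which covers laboratory results only.
- In Tables 59-60, QTcF Grades 2 and 3 already include an increase above baseline. The point there is confined to QTcF Grade 1 and PR Grades 1-2.
- Protocol 5.1 excepts ALT, AST, alkaline phosphatase, BUN, urine protein and creatinine from admission at Grade 1. Note 1 to protocol Table 3 adds bilirubin and electrolytes. Carry-over should not normally arise for these analytes.
- Under SAP 9.7, an abnormal vital sign followed by two normal repeats is analysed as normal. The row therefore takes the worst analysed grade, not the worst of every raw reading.

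The reply does not remove the core point. The row most likely to be read as a summary of toxicity mixes unchanged and worsened grades, and no other grade row separates them.

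**Conclusion.** The point holds as a limited and inexpensive improvement. The lack of any link to the participant's own baseline grade, the 9, 8 or 3 scheduled looks against one, and the mismatch with Tables 23-26 all follow from the documents without assumption.

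The size does rest on assumptions: single-session rates of 5-20% and within-person correlation of 0.3-0.9. With no drug effect, the vital-sign row would then exceed Baseline roughly 2- to 6-fold. The laboratory row would exceed it by about 1.4- to 2.6-fold, and by at most about 2.9-fold if readings were independent. The independence figures for vital signs, such as 61% at a 10% rate, are upper bounds and should not be read as expected values.

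A reader might also infer that anyone admitted at Grade 1 will almost always be counted. That is plausible for vital signs with high within-person correlation, but not for laboratory values with three draws.

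**What to change.** Keep the Baseline and per-timepoint rows as raw grades. In Tables 29-30, 35-36, 41-42, 47-48, 51-52 and 59-60, replace the Maximum Severity row with a cross-tabulation of each participant's baseline grade by worst post-baseline grade, for the same parameter and direction, or add the cross-tabulation beside it. Worsening then appears apart from carried-over grades, in line with Tables 23-26.

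Add a footnote that gives the number of scheduled times pooled (9 vital signs, 8 ECG, 3 laboratory), says that unscheduled readings are included, and warns that the maximum is not comparable with the single Baseline reading. State the rule in SAP 9.6, 9.7 and 9.8.

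Do not apply worse-than-baseline counting to the per-timepoint rows while Baseline stays raw, because that would break the one fair comparison in these tables.

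The cost is SAP wording, a few extra rows or columns and some programming. No new data are needed.

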### Table 53: Vital Sign Summary Statistics Measurement and Change from Baseline by Parameter and Timepoint – Safety Population

Table with similar format:

 Table 54:
 Vital Sign Summary Statistics Measurement and Change from Baseline by Parameter and Timepoint – Safety Subset Population

### 14.3.7 Displays of ECG Measurements

### Table 55: ECG Overall Interpretations, Post-Dose Compared to Pre-Dose Baseline by Timepoint – Safety Population

			Ch	ange from Pre-Dose Base	eline in ECG Interpretat	ion	
		Normal at Both Times	Normal to Abnormal, NCS	Normal to Abnormal, CS	Abnormal, NCS at Both Times	Abnormal, NCS to Abnormal, CS	Abnormal, NCS to Normal
Timepoint	Ν	n (%)	n (%)	n (%)	n (%)	n (%)	n (%)
Day 1, 1 h Post-Dose	х	x (xx)	x (xx)	x (xx)	x (xx)	x (xx)	x (xx)
Day 1, 4 h Post-Dose	х	x (xx)	x (xx)	x (xx)	x (xx)	x (xx)	x (xx)
Day 1, 16 h Post-Dose	х	x (xx)	x (xx)	x (xx)	x (xx)	x (xx)	x (xx)
Day 2, 24 h Post-Dose	х	x (xx)	x (xx)	x (xx)	x (xx)	x (xx)	x (xx)
Day 2, 36 h Post-Dose	х	x (xx)	x (xx)	x (xx)	x (xx)	x (xx)	x (xx)
Day 3, 48 h Post-Dose	х	x (xx)	x (xx)	x (xx)	x (xx)	x (xx)	x (xx)
Day 3, 60 h Post-Dose	х	x (xx)	x (xx)	x (xx)	x (xx)	x (xx)	x (xx)
Day 14	X	x (xx)	x (xx)	x (xx)	x (xx)	x (xx)	x (xx)
Notes: N = Number of participan CS = Clinically Significant. NCS	ts in the Safet S = Not Clinics	y Population with the ECC ally Significant.	b measurement assessed at	t the respective timepoint. I	Pre-Dose Baseline = The 1	nost recent measurement	prior to start of infusion.

Table with similar format:

 Table 56:
 ECG Overall Interpretations, Post-Dose Compared to Pre-Dose Baseline by Timepoint – Safety Subset Population

		(	Change from Pre-Dose Baseline	
		No Change from Baseline	NCS, Change from Baseline	CS, Change from Baseline
Timepoint	Ν	n (%)	n (%)	n (%)
Day 1, 1 h Post-Dose	х	x (xx)	x (xx)	x (xx)
Day 1, 4 h Post-Dose	х	x (xx)	x (xx)	x (xx)
Day 1, 16 h Post-Dose	х	x (xx)	x (xx)	x (xx)
Day 2, 24 h Post-Dose	х	x (xx)	x (xx)	x (xx)
Day 2, 36 h Post-Dose	х	x (xx)	x (xx)	x (xx)
Day 3, 48 h Post-Dose	х	x (xx)	x (xx)	x (xx)
Day 3, 60 h Post-Dose	х	x (xx)	x (xx)	x (xx)
Day 14	х	x (xx)	x (xx)	x (xx)
Notes: N = Number of participar = The most recent measurement	nts in the Safety prior to start of	Population with the ECG measu infusion. CS = Clinically Signifi	rement assessed at the respective t cant. NCS = Not Clinically Signifi	imepoint. Pre-Dose Baseline cant.

### Table 57: ECG Summary in Change from Pre-Dose Baseline by Timepoint – Safety Population

Table with similar format:

# Table 58:ECG Summary in Change from Pre-Dose Baseline by Timepoint – Safety Subset
Population

### Table 59: ECG Toxicity Grade by Parameter, Timepoint, and Severity – Safety Population

[Implementation Note: If there is not at least one mild, moderate, or severe result with a parameter, then only the "Baseline" and "Maximum Severity Post Baseline" rows will be shown for that parameter. ECG parameters without grading criteria are not included in this table.]

			Mi Gra	ild / 1de 1	Moderate/ Grade 2		Severe/ Grade 3	
Parameter	Time Point	Ν	n	%	n	%	n	%
Any Parameter	Baseline	х	х	XX	х	xx	х	xx
	Maximum Severity Post Baseline	х	х	XX	х	xx	х	xx
	Day 1, 1 h Post-Dose	х	х	XX	х	XX	х	xx
	Day 1, 4 h Post-Dose	х	х	XX	х	XX	х	xx
	Day 1, 16 h Post-Dose	х	х	xx	х	xx	х	xx
	Day 2, 24 h Post-Dose	х	х	xx	х	xx	х	xx
	Day 2, 36 h Post-Dose	х	х	xx	х	xx	х	xx
	Day 3, 48 h Post-Dose	х	x	xx	х	xx	х	xx
	Day 3, 60 h Post-Dose	х	х	xx	x	xx	x	xx
	Day 14	х	х	xx	х	xx	х	xx
QTcF Interval	Baseline	х	x	xx	х	xx	х	xx
	Maximum Severity Post Baseline	х	x	xx	х	xx	х	xx
		х	х	xx	х	xx	х	xx
		x	х	xx	x	xx	x	xx
Notes: N = Number o	f participants in the Safety Population with	the ECG me	asurement a	ssessed at tl	he respectiv	ve timepoint	t. Pre-Dose	Baseline

Notes: N = Number of participants in the Safety Population with the ECG measurement assessed at the respective timepoint. Pre-Dose Baseline = The most recent measurement prior to start of infusion. The "Maximum Severity Post Baseline" rows indicate the maximum severity experienced by each participant at any time point post baseline, including unscheduled assessments.

Table with similar format:

